#### **9.1.6. End of Treatment Visit**

Unless a subject withdraws consent from study participation, an End of Treatment Visit is to be scheduled 30 days ± 5 days after the last dose of any study drug. Every effort should be made to conduct the End of Treatment Visit before the subject starts any subsequent therapy. If a subject is unable to return to the site for the End of Treatment Visit, then the subject should be contacted to collect adverse events that occurred within 30 days after the last dose of any study drug. Additional information on reporting of adverse events can be found in Section 12. If the End of Sequential Treatment Visit is within 3 days of the End of Treatment Visit Hematology and Chemistry lab assessments do not need to be repeated.

#### **9.1.7. Follow-up Phase**

The Follow-up Phase will begin after the completion of the End of Treatment Visit. Follow-up assessments will be performed as specified in the Time and Events Schedule. Follow up visits will be performed every 3 months during the Follow-up Phase and will record disease progression, subsequent anticancer treatment including stem cell transplant, survival status, and late-occurring, potentially study-drug-related adverse events.

If the information is obtained via telephone contact, written documentation of the communication must be available for review in the source documents. If the subject has died, the date and cause of death will be collected and documented on the eCRF. Follow-up of subject data will continue for a maximum of 3 years from the enrollment of the last subject or when 80% of the patients are deceased, whichever comes first.

Investigators may contact the subject to obtain follow-up information to determine the subject's safety or survival status (refer to Section 16.2.3, Informed Consent).

## 9.2. Efficacy

### 9.2.1. Evaluations

Efficacy evaluations will be performed according to the Time and Events Schedule until transplant, disease progression, withdrawal from the study, or death. Evaluations are to be performed  $\pm 3$  days of the scheduled evaluation date (within +8 days and up to Day 42 in the case of end of cycle evaluations). If treatment has been delayed for any reason, then the disease evaluations must be performed according to appropriate point in the treatment cycle, resulting from changes to the dosing regimen. Response will be assessed using the IWG criteria as published in The Journal of Clinical Oncology, 21: 4642-4642 2003 and erratum 22: 576, 2004. Response will be evaluated prior to the start of each cycle.

Hematology including peripheral blast counts will be performed during screening, at Day 1, Day 5 (first cycle only), Day 8, Day 22 (first cycle only), and Day 28 or later if the next cycle is delayed but within 8 days of the start of the next cycle.

### Bone Marrow Examination

Bone marrow aspirate or biopsy will be performed and examined by the local laboratory at screening for clinical staging (morphology is required), at the end of Cycle 1, at the end of Cycle 2 if the subject has not attained a CR in Cycle 1, at the End of Sequential Treatment Visit, and at any time disease progression is suspected. Cytogenetic evaluations will be performed at screening. If tests such as immunophenotyping and/or cytochemical evaluations have been done for standard medical care prior or within screening period, the data will be collected in the eCRF. During the Continuation Phase, bone marrow sampling and assessments will be done as clinically indicated.

For Phase 1, bone marrow aspirates at end of Cycle 1 should be obtained no later than Day 42 in order to determine a potential DLT.

### Remission and Disease Progression/Relapse

The assessment of a response (CR or CRi), may be made only when laboratory findings meet specific criteria as defined by IWG. The timing of bone marrow assessments for efficacy endpoints will be driven by peripheral blast counts. Clinical judgment based on blood cell count recovery will dictate the exact time in each cycle when bone marrow aspirates should be taken.

Some patients may develop a relapse that leads to death quickly without having the possibility to evaluate formally the relapse of disease. Efforts should be made to obtain an autopsy report in such patients.

The dates of CR, CRi, PR, progressive disease, or any subsequent disease relapse after a response should be recorded. This should be based on the acceptable laboratory evidence from a bone marrow aspirate.

Details of the IWG criteria are given below:

## Complete Remission

For the following 2 CR categories, extramedullary leukemia, such as CNS or soft tissue involvement, must be absent. There is no stated duration of response required for a subject to be classified as a complete responder.

- **Morphologic Complete Remission (CR)**

Per the IWG criteria, CR is defined as morphologic leukemia-free state, with less than 5% blasts in aspirate sample with marrow spicules and with a count of  $\geq 200$  nucleated cells (there should be no blasts with Auer rods or any persistence of extramedullary disease), **plus** ANC  $> 1,000/\mu\text{L}$  platelet count of  $> 100,000/\mu\text{L}$  and subject must be independent of transfusions for a minimum of 1 week before each marrow assessment. No duration of response is required for CR.

- **Morphologic Complete Remission with incomplete blood count recovery (CRi)**

Per the IWG criteria, CRi is defined as morphologic CR with residual neutropenia ( $< 1,000/\mu\text{L}$ ) or thrombocytopenia  $< 100,000/\mu\text{L}$ ). No stated duration of response is required for CRi.

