## 8. PRESTUDY AND CONCOMITANT THERAPY

All prior therapies for AML must be recorded. CNS-directed intrathecal therapy administered within 30 days before the first dose of study drugs must be recorded.

Prophylactic intrathecal therapy and hydroxyurea are allowed until 1 day prior to Cycle 1 Day 1.

Concomitant therapies must be recorded throughout the study beginning with start of the first dose of study drug to 30 days after the last dose of study drug.

Concomitant therapies allowed under this protocol are:

- Packed red blood cell transfusion: transfusions may be given as clinically indicated
- Platelet transfusion: to be administered when platelets are  $<10,000/\mu L$  or according to institutional standards.
- Prophylactic antibiotics will be administered according to institutional standards.
- Management of febrile neutropenia should be in accordance with institutional standard:

Febrile neutropenia is defined as a body temperature of at least:

38.5°C on 1 occasion or 38°C on 2 occasions when the ANC is  $<1000/\mu L$ . Febrile patients are to be evaluated by physical exam, complete blood count (CBC) with differential, and blood culture. Patients with febrile neutropenia or suspected sepsis on the basis of physical exam are to be hospitalized for appropriate broad-spectrum antibiotic coverage, consistent with local pathogen sensitivities.

- Anti-emetics and other agents needed for supportive care may be given in accordance with institutional treatment standards
- Any other medications required for clinical management of the patient
- Other than the study agents, patients cannot receive other anticancer chemotherapy during this study.

The sponsor must be notified in advance (or as soon as possible thereafter) of any instances in which prohibited therapies (eg, other anticancer medications) are administered.

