## Partial Remission (PR)

Per the IWG criteria, PR is defined as all the same hematologic values of a CR, but with a decrease of  $\geq 50\%$  of the percentage of blasts to 5% to 25% in the bone marrow aspirate. Therefore, if the pretreatment bone marrow blast percentage was 50% to 100%, the percentage of blasts must decrease to a value between 5% and 25%; if the pretreatment blast percentage was 20% to less than 49%, they must decrease by at least half to a value of more than 5%. A value of  $\leq 5\%$  blasts may also be considered a PR if Auer rods are present. There is no stated duration of response required for PR.

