## Stable Disease (SD)

A subject who has no CR/CRi/PR nor has progressive disease for a period of at least 2 months should be considered stable disease (SD).

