##### **Complete Response + Complete Response with incomplete recovery rate**

In the Phase 2 portion of this study the primary end point will be the CR +CRI rate as determined using IWG criteria. The response status of each patient will be determined prior to each cycle of DACOGEN + cytarabine after the first cycle. The best response up to 4 cycles of DACOGEN + cytarabine for each subject will be used to determine the rate of CR + CRI.

To be evaluable, subjects must complete at least 2 cycles of the sequential retreatment and have at least 1 post baseline disease assessment unless disease progression or response (CR, CRI, or PR) occur prior to the planned disease assessment but after Cycle 1 treatment (ie, after Day 13 of Cycle 1).

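### A child with a leukemia-free marrow, recovered counts and a red cell transfusion in the week before is neither CR nor CRi, so the primary endpoint can miss a remission

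*Combined protocol and SAP*

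**What the plan says.** The Phase 2 primary endpoint is set in Section 9.2.2: "In the Phase 2 portion of this study the primary end point will be the CR +CRI rate as determined using IWG criteria". Section 9.2.1 restates those criteria for site use.

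- **CR** combines a leukemia-free marrow (under 5% blasts, no Auer rods, no extramedullary disease) with ANC above 1,000/µL, platelets above 100,000/µL and a transfusion condition: "subject must be independent of transfusions for a minimum of 1 week before each marrow assessment". The type of transfusion is not limited.
- **CRi**: "CRi is defined as morphologic CR with residual neutropenia" (below 1,000/µL) or thrombocytopenia (below 100,000/µL). Transfusions are not mentioned.
- **PR**: "PR is defined as all the same hematologic values of a CR", with 5% to 25% blasts after a fall of at least half. Blasts of 5% or less qualify only if Auer rods are present.
- **Stable disease**: "A subject who has no CR/CRi/PR nor has progressive disease for a period of at least 2 months should be considered stable disease".

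Section 8 lists among allowed therapies: "Packed red blood cell transfusion: transfusions may be given as clinically indicated". Platelets may be given below 10,000/µL or by institutional standards. Marrows are read locally and evaluated by the investigator (Section 9.5). No central response review is described.

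**The concern.** CR and CRi should between them cover every marrow remission, because their sum is the primary endpoint. As written they do not. CR can fail on three peripheral conditions (ANC, platelets, transfusion), but CRi takes in failures on only two of them. A remission that fails CR on transfusion alone has no place in the endpoint.

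Whether that happens depends on permitted supportive care and local transfusion habits, not on the leukemia. For the child with recovered counts the error runs one way: it lowers CR + CRi. Overall response and duration of CR + CRi inherit it.

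The setting makes transfusion near a marrow foreseeable. Section 9.5 names severe myelosuppression as the main expected toxicity of cytarabine, and Section 3.2 cites a pediatric study with slower platelet recovery after DACOGEN priming. The protocol qualifies platelet counts by transfusion in the dose-delay rule (6.3.1) and the DLT definition (9.2.2), but gives no such rule for CRi.

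**Working it through.** **1. Classify four children from the text.** Each has under 5% blasts, no Auer rods and no extramedullary disease.

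| Child | Counts | Transfusion in prior week | CR | CRi | PR |
|---|---|---|---|---|---|
| A | ANC and platelets recovered | red cells | no: transfused | no: no cytopenia | no: blasts too low |
| B | ANC or platelets low | red cells or platelets | no | depends on the reading | no |
| C | recovered | none | yes | – | – |
| D | low | none | no: counts | yes | no |

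Child A is at most stable disease, and that label needs two months without progression. If CRi is read to admit B, then B is a responder while A, with the same marrow and better counts, is not.

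**2. What CRi can mean for child B.** Morphologic CR is also the name of the full CR definition. If CRi inherited all of it, CRi would require ANC above 1,000/µL and platelets above 100,000/µL together with a low ANC or platelet count, which no child can satisfy. Something must therefore be relaxed. The workable reading keeps the marrow and extramedullary conditions and relaxes the peripheral ones, which makes B a CRi. The text does not say whether transfusion independence is among those relaxed.

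**3. Reproduce Table 5 (Section 11.4).** Inputs: n = 15, uninteresting rate 20%, interesting rate 35%.

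- False positive error = P(X ≥ x | n = 15, p = 0.20)
- False negative error = P(X ≤ x | n = 15, p = 0.35)
- Exact 95% limits = 0.025 quantile of Beta(x, 16 − x) and 0.975 quantile of Beta(x + 1, 15 − x)

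All seven rows match to rounding. Those used here:

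| Responders | Rate | 95% CI | False positive | False negative |
|---|---|---|---|---|
| 3 | 20.0% | 4.3 to 48.1 | 60.2% | 17.3% |
| 4 | 26.7% | 7.8 to 55.1 | 35.2% | 35.2% |
| 5 | 33.3% | 11.8 to 61.6 | 16.4% | 56.4% |

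**4. Effect of one child.** If the child stays in the denominator, the step is 1/15 = 6.7 points.

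- 5 to 4 responders: false positive error rises from 16.4% to 35.2%.
- 4 to 3 responders: the lower bound falls from 7.8% to 4.3%. Section 11.4 asks for at least 4 responders to rule out 5%, so that benchmark is lost.

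If the child is instead non-evaluable and not replaced, 5/15 = 33.3% becomes 4/14 = 28.6%. The step is smaller, in the same direction.

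**5. Range under an assumption.** The documents do not say how often a transfusion falls in the week before a marrow. Let m be an assumed share of true responders never recorded as CR or CRi, with a true rate of 35% and n = 15. The apparent rate is 0.35 × (1 − m).

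| m | Apparent rate | P(≥ 4 responders) | P(≥ 5 responders) |
|---|---|---|---|
| 0% | 35.0% | 82.7% | 64.8% |
| 10% | 31.5% | 74.5% | 53.6% |
| 20% | 28.0% | 64.2% | 41.5% |
| 30% | 24.5% | 52.1% | 29.7% |

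At 35%, 15 × 0.35 = 5.25 responders are expected, so m = 20% is about one child (5.25 × 0.20 = 1.05).

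**The case against.** A reader might infer that any leukemia-free child given a permitted transfusion can be neither CR nor CRi. The documents do not support that: it needs a CRi that inherits the whole CR definition, which nobody could meet (step 2). On the workable reading a cytopenic, transfused child is CRi, and myelosuppression mostly produces such children. This objection stands. It reduces child B to an ambiguity and leaves child A untouched.

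A reader might also extend the gap to platelet counts held above 100,000/µL by transfusion. The platelet trigger in Section 8 is 10,000/µL or institutional standards, and nothing suggests such support would produce those counts. That extension is not relied on here.

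One transfused marrow need not be decisive. Best response over up to four cycles counts. A child without CR has a further marrow at the end of Cycle 2 and one at the end of sequential treatment, and timing follows count recovery with some latitude (9.2.1). This stands in part: scheduled marrows are few, and a child who responds well enough for transplant stops sequential treatment (10.2).

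An affected child is not always a non-responder either. Under 9.2.2, one who leaves before two cycles without recorded response or progression may be non-evaluable.

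The operative criteria are attributed to the IWG publication, and Section 11 defers details to an SAP whose text is not among the documents. Either might settle the point, and this cannot be checked here. But sites classify from Section 9.2.1, which presents itself as giving the detail.

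Finally, the analysis is descriptive, with no responder cutoff, and further development rests on all available evidence. That limits the consequence of an error; it does not make the definition complete.

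**Conclusion.** The point holds in a limited form. For child A the gap is certain on the text: the remission is not counted in CR + CRi at that assessment, and no other section resolves it. For child B the text is ambiguous, CRi is the workable reading, and the risk is inconsistent classification between local investigators.

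The size per child is known: 6.7 points when the child stays among 15, and less if the child leaves the denominator. The number of children is not known. The losses in step 5 are an illustration that assumes a true rate of 35% and no rescue by a later marrow; they do not estimate what this trial would lose. The documents do not support a claim that one, two or any other number of responders will be missed. The matter still deserves correction, because it follows from a stated rule for the primary endpoint and each child weighs heavily at this sample size.

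**What to change.** In Section 9.2.1, restate CRi as a response that meets all marrow and extramedullary conditions for CR but fails at least one of: ANC above 1,000/µL, platelets above 100,000/µL, or one week of transfusion independence. Every marrow remission then falls in CR or CRi. The change also covers counts of exactly 1,000 or 100,000/µL, which now satisfy neither definition.

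Classify from the transfusions recorded as concomitant therapy under Section 8, and confirm that the eCRF captures their dates, which that section does not mention. Report how many children are CRi only because of transfusion, and give the CR + CRi rate with them counted as non-responders as a sensitivity analysis.

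The cost is one sentence in the protocol, a matching line in the eCRF response guide and one extra table row. No procedure or clinical care changes. There are two downsides to state openly. The wording departs slightly from the definition that the protocol attributes to the IWG, since a child with recovered ANC and platelets would carry a label meaning incomplete recovery. And some remissions will rest on transfused counts, though they are labelled CRi and not CR.

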## Partial Remission (PR)

Per the IWG criteria, PR is defined as all the same hematologic values of a CR, but with a decrease of  $\geq 50\%$  of the percentage of blasts to 5% to 25% in the bone marrow aspirate. Therefore, if the pretreatment bone marrow blast percentage was 50% to 100%, the percentage of blasts must decrease to a value between 5% and 25%; if the pretreatment blast percentage was 20% to less than 49%, they must decrease by at least half to a value of more than 5%. A value of  $\leq 5\%$  blasts may also be considered a PR if Auer rods are present. There is no stated duration of response required for PR.

## Stable Disease (SD)

A subject who has no CR/CRi/PR nor has progressive disease for a period of at least 2 months should be considered stable disease (SD).

## Progressive Disease

Progressive disease is defined as:

First Cycle: Determination of progressive disease will be based on peripheral blood (PB) count, evidence of new extramedullary disease and/or the clinical judgment of the investigator. If the blast counts in PB increases by  $> 50\%$  over the pre-treatment value during the first cycle, the subject will be considered as progressive disease if a bone marrow (BM) assessment was not performed. If BM assessment has been performed in first cycle or before the start of second cycle, then a  $> 25\%$  increase in the blasts count from baseline on BM aspirate is considered progressive disease.

During the subsequent cycles, progressive disease will be defined as  $> 50\%$  increase in peripheral blast count from baseline,  $> 25\%$  increase in the blast count from baseline on BM aspirate, or clinical evidence of new extramedullary disease or the clinical judgment of the investigator. Responses for patients who complete 3 or more cycles and never had a post-baseline bone marrow evaluation will be determined based on the clinical judgment of the investigator.

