##### 3.1.1. Phase 1 Portion of DACOGENAML2004

For the Phase 1 portion of the study, a “rolling 6” design is used. The total number of participants is dependent upon the number of cytarabine dose levels tested; the maximum number of which is 3 dose levels (1 g/m^2, 2 g/m^2, and 1.5 g/m^2) with a maximum of 18 evaluable subjects.

The MTD for cytarabine is based on the number of subjects experiencing a DLT by the end of Cycle 1. A non-hematological DLT is defined as: any Grade  $\geq 3$  toxicity that persists for  $>5$  days or any Grade 2 toxicity that persists for  $>7$  days and that is intolerable to the subject. A hematological DLT is defined as Grade 4 neutropenia or thrombocytopenia due to a hypoplastic bone marrow at Day 42, in the absence of malignant infiltration. The nominal duration of each cycle will be 28 days. However, patients who have not experienced bone marrow recovery at Day 28 will be followed up to Day 42. Failure of marrow recovery (improvement to Grade 3) by Day 42 will be considered a DLT. The maximum duration of Cycle 1 will therefore be 42 days.

The decision to dose escalate from the starting dose of 1 g/m^2 will be based on the number of subjects evaluable and the number pending evaluation during the first cycle. No dose escalation will occur unless a minimum of 3 subjects are fully evaluable with no dose limiting toxicity. If any additional subjects have been treated at that dose level, they must become evaluable before the dose can be escalated. The only exception is the setting in which 5 patients are evaluable, no DLT has been observed and data for one subject is incomplete making it impossible for the MTD to be exceeded. Further details of the “rolling-6” design and the determination of the MTD are provided in Section 6.3.

The decision to escalate or de-escalate dose levels and the identification of the MTD will be the responsibility of a Study Evaluation Team (SET) that will convene periodically based on the number of evaluable patients and the occurrence of dose limiting toxicities. The SET consists of the sponsor’s statistician and clinician and other members as needed, eg, clinical pharmacologist, safety physician. The SET will also include the lead investigator or designee from each country where the study is being conducted. Further description of the SET and their responsibilities is provided in Section 11.9.

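### The rule for patients with 3 or more cycles and no post-baseline marrow does not limit investigator judgment to stable or progressive disease, so read literally it conflicts with the marrow-based CR, CRi and PR definitions

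*Combined protocol and SAP*

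**What the plan says.** Section 9.2.1 of the protocol sets out the response categories one after another.

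- **Remission and Disease Progression/Relapse.** An assessment of CR or CRi "may be made only when laboratory findings meet specific criteria as defined by IWG". On the recorded dates of CR, CRi, PR, progression and relapse it adds: "This should be based on the acceptable laboratory evidence from a bone marrow aspirate".
- **Complete Remission.** CR needs "less than 5% blasts in aspirate sample with marrow spicules", plus neutrophil and platelet recovery. CRi is a morphologic CR with residual cytopenia, so it rests on the same marrow finding.
- **Partial Remission.** PR is also read from the aspirate. For a patient with 50% or more blasts before treatment, "the percentage of blasts must decrease to a value between 5% and 25" per cent.
- **Stable Disease.** This is the residual category: a subject with no CR, CRi or PR "nor has progressive disease for a period of at least 2 months should be considered stable disease".
- **Progressive Disease, last sentence.** Its subject is "Responses for patients who complete 3 or more cycles", without naming a category. It then provides that the outcome for those among them who "never had a post-baseline bone marrow evaluation will be determined based on the clinical judgment of the investigator".

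Footnote m of the Time and Events Schedule ties response assessment to the time of the aspirate. Sections 3.1.2 and 9.2.2 put response assessment and the Phase 2 primary endpoint, CR + CRi, on IWG criteria. Evaluability in Section 9.2.2 asks for two cycles and one disease assessment after baseline, with an exception for early progression or response. It does not say that the assessment must include a marrow.

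**The concern.** The closing sentence is a specific rule for a specific group, and it hands their response to the investigator without saying which categories are open. A patient in that group cannot satisfy the definitions of CR, CRi or PR, because each needs a marrow result that does not exist. If the sentence is applied as written, an investigator could report a CR or CRi on clinical grounds. Because evaluability is worded as a disease assessment, that patient could be counted in both the denominator and the numerator of the primary endpoint.

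Phase 2 is open-label and single-arm. A CR called with a marrow leaves a laboratory result that can be compared with the definition; a CR called on judgment alone leaves none. With about 15 evaluable subjects, one such call is visible in the reported rate.

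**Working it through.** **1. Can both rules apply to the same patient?** Take a patient who has completed three cycles and has no marrow after baseline.

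| Category | Evidence required in Section 9.2.1 | Assignable without a marrow? |
|---|---|---|
| CR | Blasts below 5% in the aspirate, plus counts | No |
| CRi | Morphologic CR with residual cytopenia | No |
| PR | Blast reduction measured in the aspirate | No |
| SD | None of the above and no PD for 2 months | Yes |
| PD, later cycles | Peripheral blasts, marrow, extramedullary disease or investigator judgment | Yes |

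The closing sentence is consistent with the rest of the section only if it is confined to the last two rows. No such limit is written.

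**2. Does the SD duration hold for these patients?** Section 3.1.1 states: "The nominal duration of each cycle will be 28 days". Three cycles are 3 × 28 = 84 days, against about 61 days for two months. Every patient the sentence covers therefore meets the duration at nominal cycle length, and SD or PD is always available.

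**3. How could such a patient arise?** The Bone Marrow Examination subsection schedules a marrow at the end of Cycle 1, at the end of Cycle 2 unless CR was attained in Cycle 1, and at the End of Sequential Treatment Visit. Without a marrow no CR by definition was attained in Cycle 1, so the Cycle 2 marrow was due. The patient has missed at least two scheduled marrows, and a third if the End of Sequential Treatment Visit was reached. A patient who died or withdrew after Cycle 3 may not have reached it.

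**4. Reproducing Table 5 (Section 11.4).** Inputs: N = 15, uninteresting rate 20%, Clopper-Pearson 95% limits. Lower limit = 2.5% quantile of Beta(x, 16 − x); upper limit = 97.5% quantile of Beta(x + 1, 15 − x); false positive = P(X ≥ x) for X ~ Binomial(15, 0.20).

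| x | Rate % | Exact 95% CI % | False positive % |
|---|---|---|---|
| 1 | 6.7 | 0.17 to 31.95 | 96.5 |
| 2 | 13.3 | 1.66 to 40.46 | 83.3 |
| 3 | 20.0 | 4.33 to 48.09 | 60.2 |
| 4 | 26.7 | 7.79 to 55.10 | 35.2 |
| 5 | 33.3 | 11.82 to 61.62 | 16.4 |
| 6 | 40.0 | 16.34 to 67.71 | 6.1 |
| 7 | 46.7 | 21.27 to 73.41 | 1.8 |

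These agree with the printed table to rounding, as does its false negative column. The table's arithmetic is not in question.

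**5. Effect of one such patient, evaluable either way.** The rate moves by 1/15 = 6.7 points, one row of the table. For moves from 1→2 to 6→7 responders, the lower limit rises by 1.5, 2.7, 3.5, 4.0, 4.5 and 4.9 points. The false positive figure falls by 13.2, 23.1, 25.0, 18.8, 10.3 and 4.3 points. The largest false positive shift is from 3/15 (lower limit 4.3%, false positive 60.2%) to 4/15 (7.8%, 35.2%).

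**6. Effect if the patient would otherwise be non-evaluable and is not replaced.** The contrast is then x/14 against (x + 1)/15, and (x + 1)/15 − x/14 = (14 − x)/210. At x = 3 this is 3/14 = 21.4% against 4/15 = 26.7%, a difference of 11/210 = 5.2 points. If the patient is replaced, the difference depends on the replacement's outcome.

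**The case against.** The best defence is that the endpoint definition already settles the matter. The wording that governs CR and CRi is restrictive, the primary endpoint is tied to IWG criteria, and a CR without an aspirate fails those criteria whatever the closing sentence says. That sentence sits under Progressive Disease, directly after investigator judgment has been named as a ground for progression. On that reading it concerns only SD and PD, and nothing conflicts. Section 11 also leaves details to a Statistical Analysis Plan; no separate SAP text is in the combined document, and a limit stated there would close the point.

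Much of this stands. The SD/PD reading is the likely intent. It is still an inference: the text never states it. The preceding sentence already gives later-cycle progression to investigator judgment and SD is residual, so a sentence confined to SD and PD adds little. A reader looking for its purpose could extend it, particularly since the remission subsection itself uses the word response for CR or CRi.

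A second objection is that the Table 5 shifts describe any one extra responder, from whatever cause, and say nothing about how often this sentence would matter. That is right. The documents give no expected number of such patients.

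A third is that a patient without a marrow may not be evaluable at all, because footnote m ties response assessment to the aspirate. Section 9.2.1 also says that response is evaluated before each cycle, which points the other way. The question is open, so the 6.7-point figure has to carry the condition that the patient is evaluable either way.

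**Conclusion.** The closing sentence of the Progressive Disease subsection is a stated rule that, taken literally, conflicts with the marrow requirements for CR, CRi and PR and with an IWG-based primary endpoint. The conflict is minor.

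Its size is 6.7 points per affected patient at N=15 if the patient is evaluable either way. It is smaller (5.2 points in the 3/14 against 4/15 example) if the patient would otherwise be non-evaluable and is not replaced. It is zero if the marrow schedule is followed.

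A reader might infer that the protocol lets investigators declare remissions without a marrow and that the primary result is therefore unreliable. The documents do not support that: the other subsections point firmly the other way, an SD/PD intent is likely, and such patients should be rare. Nor does moving from 3 to 4 responders cross a decision boundary. Section 11.4 uses the exclusion of a 5% rate as an illustration, plans no hypothesis test, and rests the development decision mainly on the whole body of evidence from this and other studies.

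**What to change.** Replace the closing sentence with wording to this effect: where a patient has completed three or more cycles without any marrow examination after baseline, investigator judgment serves only to separate progressive from stable disease; CR, CRi and PR require a post-baseline marrow that meets the Section 9.2.1 criteria.

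Add that these patients, if evaluable under Section 9.2.2, count as non-responders for both CR + CRi and CR + CRi + PR, and that they are listed individually in the study report.

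The cost is one sentence replaced and one added, with no new procedure or visit. The downside is that the observed rate may come out slightly lower if any such patient would have been called a responder. If there is none, nothing changes.
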